### 3.3 SUB-STUDY OBJECTIVES

There are three objectives for the sociobiological response sub-study that is being conducted as part of this trial.

- To evaluate the effects of stress reactivity on the development of an effective anti-tumor immune response in this patient population
- To evaluate the difference in terms of stress reactivity based on SES, perceptions of social stressors, and AL between racial subgroups.
- To evaluate the difference between racial subgroups for the magnitude and distribution of stress responses with biological (AL) and immunologic measure of vaccine effect.

## 4 INVESTIGATIONAL PLAN

### 4.1 STUDY DESIGN AND DURATION

This will be a Phase II study of adjuvant PROSTVAC-V/F in subjects at high risk for relapse after radical prostatectomy. The study will be carried out at MUSC and the VAMC. The coordinating center will be at the Sponsor-Investigator Support Unit. Additional sites may be recruited as needed to ensure accrual.

We anticipate a two year period of accrual and an equal period of follow up for each subjects, or approximately four years total, from the point of completions of approvals and contracts.

The study population will be post-prostatectomy patients whose pathology reports documents one or more high risk features, including one or more of the following: pT3b or pT4, pN1, pT3a (without adjuvant radiation), positive margins, pre-operative PSA  $\geq 10$  ng/mL, Gleason score 8-10. Each site PI will be responsible for reviewing all prostatectomy cases to determine the patient's eligibility and interest in participating in the study.

Forty evaluable subjects (total 44 subjects) will be enrolled. Subjects will be treated with PROSTVAC-V/F alone. Subjects will be followed for relapse for two years after prostatectomy.

Prior to any study specific activities, the patient must be aware of the nature of his/her disease and willingly consent to the study after being informed of study procedures, the experimental therapy, possible alternatives, risks and potential benefits. IRB approval of this protocol and accompanying consent is required.

### 4.2 PATIENT POPULATION

This study will be conducted at MUSC and the VAMC. There are approximately 80 radical prostatectomies performed yearly at MUSC (30% African American), and 70 at the VAMC (70% African American). Both institutions have extensive experience with prostate cancer clinical trials, and investigators have been particularly successful in recruiting African American subjects. Therapeutic trial accruals in the HCC include approximately 25% African American subjects, reflecting a close match to the 30% prevalence of African Americans in the population of South Carolina. This study will aim to enroll equal numbers of African American and Caucasian subjects.

#### 4.3 INCLUSION CRITERIA

1. Age  $\geq 21$
2. Completed radical prostatectomy for pathologically-verified adenocarcinoma of the prostate no more than 120 days prior to start of treatment. The following procedures are acceptable: radical retropubic prostatectomy (RRP), laparoscopic radical prostatectomy (with or without robotic assistance; LAPD), radical perineal prostatectomy (RPP).
3. Post-operative PSA  $< 0.2$  ng/mL by 120 days after prostatectomy
4. Must have one or more of the following:
  - pT3b or pT4 primary tumor
  - Gleason score 8-10
  - pN1 lymph node disease
  - positive surgical margins
  - pre-operative PSA of  $\geq 10$  ng/mL
  - presence of any tertiary Gleason 5 component on the prostatectomy pathology report.

**Note:** Patients with pT3a disease who lack one of the above criteria, and who refuse adjuvant radiation, may also be enrolled.

5. ECOG performance status 0-1
6. Adequate hematologic, renal, liver function per parameters in Table 1
7. Subject of fathering potential must agree to use an adequate method of contraception to avoid conception throughout the study and for at least 4 weeks after the last dose of study drug to minimize the risk of pregnancy.
8. Subjects must have had a negative bone scan, and CT of abdomen and pelvis within 26 weeks prior to registration. Additional forms of imaging (Prostascint scan, MRI) may be substituted for a CT scan of the abdomen and pelvis if clinically indicated.

**Table 1. Organ Function Criteria**

Table 1. Organ Function Criteria

• Total bilirubin <math>< 1.5 \times</math> ULN

• Hepatic enzymes (AST, ALT) <math>\leq 2.5 \times</math> ULN

• Serum sodium, potassium, and calcium <math>\geq</math> LLN

• Serum Creatinine <math>\leq 1.5 \times</math> ULN

• Hemoglobin <math>\geq 9</math> gm/dL

• Neutrophil count <math>\geq 1000/\text{mcL}</math>

• Platelets <math>\geq 100,000/\text{mcL}</math>

- Total bilirubin  $< 1.5 \times$  ULN
- Hepatic enzymes (AST, ALT)  $\leq 2.5 \times$  ULN
- Serum sodium, potassium, and calcium  $\geq$  LLN
- Serum Creatinine  $\leq 1.5 \times$  ULN
- Hemoglobin  $\geq 9$  gm/dL
- Neutrophil count  $\geq 1000/\text{mcL}$
- Platelets  $\geq 100,000/\text{mcL}$

#### 4.4 EXCLUSION CRITERIA

1. Pure small cell carcinoma of the prostate
2. Radiographically-demonstrable metastases at any time prior to the time of enrollment

3. Diagnosis of cancer requiring systemic therapy in the past 5 years
4. Presence of any major medical condition which, in the opinion of the investigator, precludes participation in the study
5. Neoadjuvant or adjuvant therapy of any kind
6. Chronic administration (defined as daily or every other day for continued use > 14 days) of systemic glucocorticoids within 28 days of the first planned dose of PROSTVAC-V/F. Use of inhaled steroids, nasal sprays, and all topical preparations (creams, solutions, gels, ointments, etc.) for up to 5% of the body surface area is allowed.
7. Use of systemic immunosuppressant agents including anti-metabolites, glucocorticoids, TNF $\alpha$  antagonists, antibodies to IL6 or IL6R, calcineurin inhibitors, mTOR antagonists
8. Prior history of serious toxicity or a systemic reaction to vaccinia immunization such as myopericarditis progressive vaccinia infection, or eczema vaccinatum.
9. Inflammatory or exfoliative skin diseases such as eczema, psoriasis that disrupt epidermis
10. Active infections requiring systemic therapy
11. Serologic evidence of HIV/AIDS.
12. Positive hepatitis C serology or active hepatitis B infection.
13. History of allergy to eggs, egg products, aminoglycoside antibiotics
14. History of myocardial disease, such as myocarditis, cardiomyopathy, congestive heart failure, ischemic cardiomyopathy
15. Prior solid organ or stem cell transplant
16. History of or active autoimmune disease (e.g., autoimmune neutropenia, thrombocytopenia, or hemolytic anemia, systemic lupus, localized lupus, Sjogren's syndrome, scleroderma, myasthenia gravis, Goodpasture's syndrome, or Addison's disease). Persons with vitiligo, Hashimoto's thyroiditis, or Graves disease are not excluded.
17. Vaccination with live attenuated vaccine within 28 days prior to day 1 of PROSTVAC-V/F administration or vaccination with a killed vaccine within 14 days prior to day 1 of PROSTVAC-V/F.
18. Inability to avoid close contact or household contact with the following high-risk individuals for three weeks after the Day 1 vaccination or until the vaccination site heals completely: (a) children  $\leq$  3 years of age; (b) pregnant or nursing women; (c) individuals with prior or concurrent extensive eczema or other eczemoid skin disorders; or (d) immunocompromised individuals, such as those with HIV.

19. Any condition which, in the opinion of the investigator, would prevent full participation in this trial (including Follow-Up), or would interfere with the evaluation of the trial endpoints.

#### **4.5 ELIGIBILITY FOR THE OPTIONAL SUB-STUDY**

Patients who are being screened for the therapeutic clinical trial will also be approached for participation into the optional sub-study evaluating sociobiological response to stress. Refusal to participate in the sub-study will not impact the patient's eligibility to participate in the therapeutic intervention.

Should a patient consent to the optional sub-study, the patient may proceed with the optional baseline interventions for the optional sub-study as outlined within the protocol's study calendar.

#### **4.6 SUBJECT ENROLLMENT AND REGISTRATION**

The SIS Unit will provide patient registration services for the optional sub-study and for the main study.

The SIS Unit will conduct a patient eligibility audit review of all eligibility source documents prior to patient registration. After obtaining signed informed consent(s) and completion of required baseline assessments, eligible subjects will be registered. A unique subject number will be assigned to each patient. The SIS Unit will issue a patient registration confirmation email to the enrolling study team at the time of registration. This confirmation will include the patient's assigned treatment regimen and study ID number. If the patient consented to the optional sub-study, the ID used for that portion of the study will be the subject's study ID. Patient registrations may occur between 8AM and 5PM EST, Monday through Friday.

#### **4.7 DISCONTINUATION OF SUBJECTS FROM STUDY**

Subjects must discontinue study treatment and withdraw from the study or optional sub-study for any of the following reasons:

- Withdrawal of informed consent (subject's decision to withdraw for any reason)
- PCa relapse at any time after completion of PROSTVAC administration (see 7.5 for definition)
- Any clinical adverse event (AE), laboratory abnormality, or intercurrent illness which, in the opinion of the investigator, indicates that continued participation in the study is not in the best interest of the subject
- Termination of the study by BNI
- Loss of ability to freely provide consent through imprisonment or involuntarily incarceration for treatment of either a psychiatric or physical (e.g., infectious disease) illness
- Initiation of any form of non-protocol cancer treatment
- Initiation of scheduled narcotics for pain treatment

- Unacceptable toxicity defined as any grade 3-4 possibly or definitely related non-hematologic toxicity that does not improve to grade 1 or resolve within 28 days or any possibly or definitely related grade 3-4 hematologic toxicity that does not improve to grade 1 or resolve with 14 days.

General or specific changes in the patient's condition render the patient unacceptable for further treatment in the judgment of the investigator.

## 5 **TREATMENTS**

### 5.1 STUDY TREATMENT: PROSTVAC-V/F

Subjects must start study drug within 120 days after surgery.

#### 5.1.1 Identification, Packaging, and Labeling

PROSTVAC-V/F is comprised of two components. PROSTVAC-V is a replication-competent vaccinia virus which has been engineered to encode the sequences for a modified human PSA and a TRICOM. PROSTVAC-F is a fowlpox virus which does not replicate in human cells and has been engineered to encode the same sequences present in PROSTVAC-V. A full description of the PROSTVAC-V/F product and PROSTVAC-V/F pre-clinical and clinical support are contained in the IB. Study vaccine for this trial contains no preservatives or adjuvants and is supplied in single-dose 2 ml clear, borosilicate glass injection vials with rubber injection stoppers covered by a plastic-aluminum flip cap.

#### Active Ingredient:

- PROSTVAC-V: PROSTVAC-V-PSA-TRICOM in aqueous solution for injection
- PROSTVAC-F: PROSTVAC-F-PSA-TRICOM in aqueous solution for injection

**Product Description:** PROSTVAC-V/F is comprised of two recombinant pox viruses: a recombinant vaccinia virus (PROSTVAC-V) and a recombinant fowlpox virus (PROSTVAC-F). Both recombinant pox viruses contain genes for human PSA, B7.1, ICAM-1, and LFA-3. The PSA gene used in these recombinants has an alteration in an HLA-A2 specific epitope (replacement of isoleucine with leucine at amino acid position 155; designated L155). In PROSTVAC-V, all four genes are inserted into the genome of a derivative of the Wyeth strain of vaccinia virus (strain NYCBH). In PROSTVAC-F, all four genes are inserted into the genome of a plaque-purified isolate of the POXVAC-TC vaccine strain of fowlpox virus.

The PROSTVAC-V/F study vaccines are manufactured at IDT's GMP facility in Dessau-Rosslau, Germany in compliance with cGMPs. The formulations do not contain adjuvants or preservatives. The study drug substance is thawed and formulated by dilution in PBS in 10% glycerol. 0.7 ml of the formulated material is dispensed aseptically into sterile 2 mL clear borosilicate glass vials, the vials are sealed with rubber injection stoppers and plastic/aluminum flip-caps, and a label is affixed to the vial. PROSTVAC-V/F study vaccine vials are then packaged in 6-vial cartons with an outer carton label.

#### 5.1.2 Storage, Handling, and Dispensing

**Storage\*:** -70°C or below

Storage conditions and stability claims for the final PROSTVAC-V/F product are based on long-term manufacturing experience with PROSTVAC-V/F by Therion, the initial manufacturer. The stability data for PROSTVAC-V/F shows virus titer stability for four years when stored at -80°C ( $\pm 10^{\circ}\text{C}$ ).

PROSTVAC-V/F will be ordered by participating sites directly from the manufacturer.

## 5.2 SELECTION AND TIMING OF DOSE FOR EACH SUBJECT

### 5.2.1 PROSTVAC-V/F Treatment

All subjects will receive PROSTVAC V/F in the same dose and schedule.

**Drug Administration:** Doses of PROSTVAC-V/F will be drawn into labeled syringes by a research pharmacist or designee for use by the clinic staff. PROSTVAC-V will be administered by the designated study staff once by subQ injection on one side (upper arm or upper outer thigh) on Day 1. PROSTVAC-F will be administered by the study staff six times by subQ injection on Days 15, 28, 57, 85, 113 and 141. Vaccination with PROSTVAC-F will begin on one side (upper arm or upper outer thigh), and subsequent immunization sites should be rotated to the opposite side and/or limb if possible. The doses will contain the following:

- 0.5 ml containing at least  $2 \times 10^8$  Infectious Units (Inf.U) PROSTVAC-V
- 0.5 ml containing at least  $1 \times 10^9$  Inf.U PROSTVAC-F

Subjects should be informed on how to care for the wound after each injection of the study agent.

**Dose Modification or Interruptions:** There will be no modification or delays in dosing of PROSTVAC V/F for toxicity. If there are unresolved toxicities related to PROSTVAC V/F at the time the next dose is due, the patient should be taken off study. PROSTVAC V/F treatment should be initiated within 120 days after prostatectomy. If there is a delay due to scheduling, within the  $+\text{-} 7$  days window, it will be at the investigator's discretion whether to have the subject continue.

## 6 CONCOMITANT TREATMENTS

### 6.1 PROHIBITED AND/OR RESTRICTED TREATMENTS

- Subjects may not receive any other form of anti-cancer therapy during this study except for PROSTVAC V/F.
- Daily use of finasteride, dutasteride, is not permitted during this study
- Use of supplements reported to delay progression of prostate cancer (vitamin D3 over 1000IU daily, pomegranate juice or extract, lycopene) is not permitted.
- Testosterone, estrogen agonists (estradiol, diethylstilbestrol), progesterone agonists, or DHEA-containing medicines or supplements is not permitted during the study.

## 6.2 OTHER RESTRICTIONS AND PRECAUTIONS

- Subjects should not start treatment with any immunosuppressive agents during study. This includes daily oral or parenteral glucocorticoids, antimetabolites, calcineurin inhibitors, mTOR inhibitors, cytokine antagonists.
- Subjects should not receive live attenuated vaccine within 28 days prior to PROSTVAC-V/F administration or a killed vaccine within 14 days prior to or after completion of PROSTVAC-V/F.

## 6.3 TREATMENT COMPLIANCE

Treatment compliance for PROSTVAC V/F will be ensured by administration of the agent in the treating physician's office or infusion center.

## 7 STUDY ASSESSMENTS AND PROCEDURES

Scheduled treatments, procedures, and assessments are shown in the table contained in [Appendix A](#).

### 7.1 THERAPEUTIC TRIAL PROCEDURES

A variety of clinical assessments are made during the screening period and while the subject is on study. These include the following. Specific details about the timing of these procedures can be found in the study calendar ([Appendix A](#)):

- Patients will be given instructions on how to care for the injection site after each injection of PROSTVAC-V and PROSTVAC-F.
- History and physical examination. The history includes a review of the prostatectomy pathology report to ensure that it includes the following information: date of surgery, subject's age at surgery, pre-op PSA, Gleason score, margin status, extraprostatic extent, seminal vesicle status, lymph node status. A measurement of the PSA at 45 or more days after surgery is also necessary, if the post-prostatectomy PSA nadir is not < 0.2 ng/mL before then.
- CBCD
- CMP (sodium, potassium, chloride, bicarbonate, BUN, creatinine, glucose, albumin, alkaline phosphatase, AST, ALT, calcium);
- Lipid Panel (total cholesterol, HDL cholesterol, triglycerides, LDL cholesterol, non-HDL cholesterol). Lipid panel will only be done at baseline and requires patients to be fasting. If a fasting blood draw cannot be done at screening (prior to registration), it may be done on day 1 prior to agent administration.
- PSA
- Testosterone
- C-reactive protein
- HIV, Hep B and Hep C serology screening, unless known negative within previous 2 years prior to registration.

- Scans: Technetium bone scan (but not F-fluoride PET scan); CT scan of abdomen, pelvis (a Prostascint scan or MRI of abdomen, pelvis can be substituted). Scans can be done up to 26 weeks prior to start of treatment.

Correlative research will include the following:

- FACT-P, AUA SS, and SHIM quality of life questionnaires
- Collection of blood for research (refer to Section 8):
  - 10 mL blood in a sodium heparin tube
  - 7 mL blood in a lithium heparin tube
  - 21 mL blood in a EDTA tube
  - 7 mL blood in a serum (clot) tube
- FFPE tissue, if available: 5 thick (20 micron) sections on plastic slides for genomic analysis, plus 5 additional thin (5 micron) sections
- Social Determinants Survey: Patients will be given the option to complete the survey via telephone administration or in-person during the clinic visit of their first vaccine treatment. Surveys that are completed over the telephone will be administered by a trained research assistant from MUSC to obtain information on SES and to measure social factors (e.g., perceived loneliness), perceived stress, behavioral factors (i.e. exercise and diet), shared decision-making with providers, and knowledge and perceptions about precision medicine. Surveys completed during the clinic visit will be self-administered. The survey will take 30 minutes to complete.

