Because of the logistics for scheduling and the TSST assessment, the timeframe for conducting the assessment may be prior to the main study registration. The TSST must be administered after the patient provides consent to the optional sub-study and any time before the patient begins PROSTVAC treatment. The TSST experimental stress challenge should begin at 4:00 pm. During the TSST, participants are told at 4:00 pm that he will soon perform to an audience which includes a speech and arithmetic task. The topic of the speech is why he should be hired for a particular job (the individual's "dream job"). The participant will deliver the speech as though speaking to a group of hiring managers. The experimenter then tells the participant that he has five minutes to prepare the speech, and starts the countdown clock (which is placed in view of the individual). The experimenter leaves the room to allow the participant to prepare. At 4:33 pm, the participant is escorted by the experimenter to an interview room, where three individuals unfamiliar to the participant (the audience) are seated; the individual is instructed by one audience member (the spokesperson) to stand and begin his prepared speech (without notes).

The speech is delivered for five minutes. At the end of the speech task (4:44 pm), the individual is instructed to serially subtract 13 from 1,022 as quickly and accurately as possible. If the

participant makes a mistake, he is told to begin again at 1,022. The mental math recitation continues for five minutes, at the end of which time, the spokesperson instructs the individual to stop. The experimenter enters the room and escorts the participant back to the initial room. The TSST, in total, spans 10 minutes. The first post-stressor assessment occurs immediately following the task (or control condition) at 4:46 p.m. and the last post-stressor assessment occurs at 5:10 p.m.

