## 8.6 ALLOSTATIC LOAD

Allostatic load will be determined based on laboratory results and clinical measures that will

Figure 3. TSST Procedures and Timeline		
TIME	EXPERIMENTAL PROCEDURE	STRESS ASSESSMENT
4:00-4:15pm	Acclimation period (15 minute duration)	Patient arrives and given relaxation tools (i.e. spa video, magazine, nature scenes)
4:16 Baseline (immediately following acclimation period)	Laboratory Stress measurements	Take cortisol, BP, HR, and assess SUD
4:28pm Immediately before TSST (12 minutes following baseline)	Laboratory Stress measurements	Take cortisol, BP, HR, assess SUD, and explain the task and give participant paper to write notes
4:33- 4:44pm (5 minutes following 2 nd lab measurements)	TSST	
5 minutes	Interview task	
5 minutes	Arithmetic task	
Post TSST stress assessments (12 minute increments)		
4:46pm Post TSST (2 minutes following TSST)	Post-TSST Assessment	Cortisol, BP, HR, SUD
4:58pm 12 mins post TSST	Post-TSST Assessment	Cortisol, BP, HR, SUD
5:10pm 24 mins post TSST	Final Post-TSST Assessment	Cortisol, BP, HR, SUD
Note: Patients more than 15 minutes late are unable to participate in the TSST and would need to be rescheduled.		

include the following; blood pressure, heart rate, total cholesterol, HDL cholesterol, body mass

index (BMI), C-reactive protein (CRP), DHEAS and interleukin-6 (IL-6). Cortisol will also be measured for those participating in the optional sub-study. We will use established methods to determine allostatic load. These methods use established clinical cutoffs to categorize biomarkers as being within normal ranges. For instance, a systolic blood pressure  $\geq 140$  mm/Hg and CRP  $\geq 3$  mg/L are values that are outside of normal ranges. The values for each biomarker will be coded into a dichotomous variable (1=above normal cutoff and 0=below normal cutoff). Scores for allostatic load will be calculated by summing dichotomous values for each biomarker.

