Descriptive statistics will be summarized for the AL measurements (e.g. median) at each time point (baseline, day 85, day 225, and day 730 or off study) for the entire patient population and for each racial group. We will compare the mean difference between two consecutive time points between two racial groups using a Wilcoxon rank sum test. A linear mixed model will also be fitted in which we will regress AL measurements on racial group, time, stress reactivity (may consider interaction terms) to explore the AL response profile difference. The outcome of RFS will be evaluated using Kaplan-Meier estimates and the statistical significance of difference in RFS between racial groups will be tested by a logrank test. In addition, a cox regression model will be explored.

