- j. If available: Send 5 thin (5 micron) sections on glass for H+E and IHC staining. These can be sent at any time after consent has been signed.
- k. Lipid panel requires patients to be fasting and can be done any time after informed consent is signed and prior to day 1 agent administration.
- l. HIV, Hep B and Hep C serology screening, unless known negative within previous 2 years prior to registration.
- m. PSA confirming eligibility can be done outside of the 30 day window. However, if PSA confirming eligibility was done greater than 30 days prior to day 1, it should be repeated prior to day 1 agent administration to ensure PSA is < 0.2ng/mL
- n. Day 1 assessments completed within 24 hours of screening assessments do not need to be repeated.
- o. Interim medical history includes any changes to the patient's medical history and/or any clinical changes since the previous clinic visit.
- p. For non-local patients in follow up, all attempts should be made to have subject return to the clinic for all follow up visits, but specifically day 225 and day 703. However, clinical care procedures (PSA, CMP, CBCD, focused physical exam and interim medical history – to include AE assessment and conmed assessment) may be done locally and the records provided. At a minimum, a PSA must be done and results provided to the study team. If a clinic visit is not done during follow up, the study team may conduct a phone interview (using the phone contact guide, Appendix D) in lieu of an clinic visit to assess adverse events, current cancer therapy and PSA level. Quality of life surveys may also be conducted over the phone by the study team if the subject does not return to clinic.
- q. Questionnaires may be mailed to the subject in pre-metered envelope if they are unable to come into the clinic to complete them (ie: due to COVID19 travel restrictions). The subject will complete the questionnaires at home and then mail the completed questionnaires back to the main site in the provided envelope.

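### Allostatic load is analysed at four time points, but two of its eight summed markers (total cholesterol and HDL) are drawn only at baseline, so the score cannot be computed as defined afterwards

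*Combined protocol and SAP*

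**What the plan says.** Section 8.6 names the markers: "blood pressure, heart rate, total cholesterol, HDL cholesterol, body mass", continuing "index (BMI), C-reactive protein (CRP), DHEAS and interleukin-6 (IL-6". That makes eight. Each is coded 0 or 1 against a clinical cutoff and the codes are added. The section gives no rule for a marker that was not measured. It adds: "Cortisol will also be measured for those participating in the optional sub-study".

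Both cholesterol markers come from one test. Section 7.1 describes it as "Lipid Panel (total cholesterol, HDL cholesterol, triglycerides, LDL cholesterol, non-HDL cholesterol" and says: "Lipid panel will only be done at baseline and requires patients to be fasting". Appendix A, note k, agrees that it "can be done any time after informed consent is signed and prior to day 1 agent administration". The off-study list in Section 7.3 contains no lipids, and Section 8.1 does not name lipids among the assays on the later research blood.

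Aim 3 in Section 10.3 plans descriptive statistics for "AL measurements (e.g. median) at each time point (baseline, day 85, day 225, and day 730 or off study". It then compares the change between consecutive time points between two racial groups by a Wilcoxon rank-sum test, and fits a linear mixed model of the score on racial group, time and stress reactivity.

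The only cortisol sampling described is at the stress test, which Section 8.5 allows "any time before the patient begins PROSTVAC treatment".

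**The concern.** The definition and the collection schedule do not fit together. Aim 3 needs the same score at four visits, and the schedule supplies all its ingredients at one. The analyst will therefore have to improvise, probably after seeing data, and the choices give different answers. The simplest choice, adding whatever is available, puts baseline on a 0-8 scale and later visits on a 0-6 scale. A man with a flagged lipid at baseline then loses that point by Day 85 without any biological change. The time term in the mixed model absorbs that loss. If flagged lipids are more common in one racial group, so does the contrast in change between groups, which is the Aim 3 question.

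**Working it through.** The plan states no power or error figure for this analysis, so there is none to reproduce. The check is a count followed by an expected-value calculation.

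**1. Count by visit.**
- Baseline: blood pressure, heart rate, total cholesterol, HDL, BMI, CRP, DHEAS, IL-6 = 8.
- Day 85, Day 225, Day 730: at most 8 - 2 = 6. By design 2/8 = 25% of the score is absent, and the maximum falls from 8 to 6.

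**2. Plain sum of available markers.** Let S0 and S1 be the sums of the six non-lipid markers at baseline and Day 85, and let p_TC and p_HDL be the shares of men flagged on each lipid. With no true change, E[S1] = E[S0], so

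E[change] = E[S1] - (E[S0] + p_TC + p_HDL) = -(p_TC + p_HDL).

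The documents give no prevalences. Over an assumed range:

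| Flagged, each lipid | Expected fall | Men with at least one flagged lipid, 1 - (1 - p)^2, if independent |
|---|---|---|
| 0% | 0 | 0% |
| 10% | 0.2 | 19% |
| 30% | 0.6 | 51% |
| 50% | 1.0 | 75% |

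The bound is 2 points. At 20-50% for total cholesterol and 20-40% for HDL, the fall is 0.4 to 0.9 points.

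**3. Other ways of handling the gap.**
- Carry baseline lipids forward: lipid contribution to change = 0.
- Prorate by 8/6, other six markers flagged at 30%: 6 x 0.3 x 8/6 - (6 x 0.3 + 2p) = 0.6 - 2p, which is +0.4, 0 and -0.4 at p = 10%, 30% and 50%.
- Treat the score as missing: no follow-up score at all.

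**4. Later steps.** Day 85 to 225 and Day 225 to 730 compare six markers with six. The lipids do not enter.

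**5. Between-race comparison, plain sum, baseline to Day 85.** The spurious group difference equals the difference in expected lipid points. At 0.7 versus 0.4 it is 0.3 points. Simulated rejection rates of the two-sided 5% rank-sum test with no true change:

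| Assumption | Rejection |
|---|---|
| 0.7 vs 0.4 lipid points, six other markers each flip with probability 0.1, 12 per group | about 10% |
| Same, 16 per group | about 13% |
| Same gap, other markers independent between visits | 6-7% |
| 0.6 vs 0.5 lipid points | about 5-5.5% |
| 30% vs 30% per lipid, 15 per group | 3.9% |
| 20% vs 40% per lipid, 15 per group | about 19% |
| 10% vs 50% per lipid, 15 per group | about 60% |

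In the 15-per-group rows the other six markers are flagged at 30% and are mostly stable between visits (1,500 runs each). With no lipid contribution the rate is 4.8%.

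**6. Cortisol.** If it is meant to enter the sum, sub-study men have nine markers at baseline, of which 3/9 are baseline-only.

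**The case against.** A reader might infer that the score must fall after baseline. The documents do not support that. Section 8.6 has no rule for unmeasured markers, and the fall follows only if the lipids are dropped or scored 0, and only through men flagged at baseline. Carrying forward produces no artefact. What stands is that the score is not computable as defined and that the plain sum is biased.

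A reader might also infer that the Aim 3 race comparison is invalid, or that the first change reflects no biology. Neither follows. Six other markers can still change, the later steps are unaffected by lipids, and with equal lipid abnormality by race the test holds its level. The documents give no racial gap in lipids, so every inflated rate above is illustrative.

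Counting cortisol as a ninth summed marker is likewise an inference. Section 8.6 says only that it is measured, and Section 8.5 describes a separate use during the acute stress response.

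Section 11.8 extracts laboratory results from health records, which might supply later lipids. It does not schedule them at these visits or say that they feed the score, and routine values need not match the visits or be fasting.

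Finally, the analysis is exploratory and tied to an optional sub-study, and Section 2.6.2 says that the trial is not powered for subtle racial differences in stress response. That limits the importance but does not remove the conflict.

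**Conclusion.** The conflict is real and rests on explicit text: the score as defined cannot be computed at three of its four analysis times. Under a plain sum, the baseline-to-Day-85 change is biased downward by p_TC + p_HDL, between 0 and 2 points, and this distorts the time effect in the mixed model. The race contrast is distorted only if baseline lipid abnormality differs by race. Rejection then ranges from near 5% for small gaps, through 10-13% at 0.7 versus 0.4 lipid points, to about 19% at 20% versus 40% per marker. All prevalences, marker stability and group sizes are assumptions. Cortisol adds a further baseline-only marker only if it is meant to be summed, which Section 8.6 leaves unclear. The primary endpoint, the futility rule and the safety rule are untouched. The point should be corrected before the sub-study data are analysed.

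**What to change.** In Sections 8.6 and 10.3:

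- Define the longitudinal score only on markers collected at all four time points. Check blood pressure, heart rate, BMI, CRP, IL-6 and DHEAS against the full calendar and assay list before naming them. CRP is absent from the off-study list in Section 7.3, DHEAS is not named among the assays in Section 8.1, and the calendar's visit marks could not be read in the text available for this review.
- Use the lipid-inclusive score for baseline analyses only.
- State that cortisol is not part of the longitudinal sum, so that all men share one scale.
- Give a rule for a marker missing at a visit. Appendix A, note p, permits local or telephone follow-up with PSA as the minimum, so blood pressure, heart rate and BMI may also be absent.

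With one fixed set of markers measured at every visit, the lipid artefact is zero. The cost is wording plus the check of what is collected, and a longitudinal score with fewer components. Repeating the fasting lipid panel at the three later time points would also resolve the mismatch, but needs extra fasting draws.
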